1. LAY SUMMARY

Why is the research important?

Dissociation involves distressing feelings of unreality and disconnection. Evidence suggests it is particularly common amongst people with existing mental health difficulties, where it has been linked with greater clinical severity, poorer treatment response, and increased self-harm and suicidality. However, there are currently no psychological treatments for dissociation that have been developed from a scientific understanding of its underpinning psychological factors. We would like to develop such a treatment. Previous research has identified potential factors, and we have developed three brief psychological interventions each targeting one factor. By precisely targeting a factor with therapy, any resulting ‘downstream’ effect on dissociation would indicate that the relationship between the factor and dissociation is causal – not just correlational. This case series will therefore test whether three factors (cognitive appraisals; worry; difficulties tolerating emotions) have a causal relationship to dissociation. This information will be crucial for building a case for support to fund larger, more rigorous tests of the factors and interventions.

What will happen in the study?

Three studies, each with four participants, will test a different psychological factor. Participants will be: adults (16+ years); on for the caseload of an NHS mental health service; high scorers on a dissociation questionnaire. Participants will complete assessments before and after treatment, and at a one-month follow-up. The studies follow a ‘multiple baseline design’, meaning that all four participants for that study will complete their baseline assessment in the same week, and then be randomly allocated to wait either one, two, three, or four weeks before starting the intervention. The intervention will consist of four therapy sessions taking place within a five-week ‘window’. Taking part in the research is voluntary. Before deciding whether to participate, we will explain the study and answer any questions.

How will results be measured?

Daily, participants will record a score for their dissociation and the psychological factor being targeted. At baseline, post-therapy, and follow-up we will also measure their levels of other factors related to dissociation (i.e. those not targeted by the therapy). Additionally, we will request feedback from participants about the therapy at the end of their involvement, in order to improve it in future.

Ultimately, if successful, these interventions could form a pilot therapy for further testing and development. We hope this would mean fewer people struggle with the challenges of dissociation.

3. ABBREVIATIONS

AE	Adverse Event
AIS	Affect Intolerance Scale ¹
AMHT	Adult Mental Health Team
CAD-P	Cognitive Appraisals of Dissociation in Psychosis scale ²
CBT	Cognitive Behavioural Therapy
ČEFSA-14	[name] Felt Sense of Anomaly Scale (Short Form) ([name] et al., in prep)
CI	Chief Investigator
CRF	Case Report Form
DBT	Dialectical Behavioural Therapy
EIP	Early Intervention in Psychosis
FSA	Felt Sense of Anomaly
GCP	Good Clinical Practice
GDPR	General Data Protection Regulation
GSE	General Self Efficacy scale ³
HRA	Health Research Authority
ICF	Informed Consent Form
ICMJE	International Committee of Medical Journal Editors
IP	Intellectual property
LEAP	Lived Experience Advisory Panel
MBD	Multiple Baseline Design
NHS	National Health Service
OAS	Online Alexithymia Scale (amended) ⁴
PIS	Participant/ Patient Information Sheet
PTQ	Perseverative Thinking Questionnaire ⁵
REC	Research Ethics Committee
RTD	Responses to Dissociation scale ⁴
SAE	Serious Adverse Event
SCED	Single Case Experimental Design
UoB	University of Birmingham
VAS	Visual Analogue Scale

4. BACKGROUND AND RATIONALE

What is dissociation?

“I was in a totally different world; it was going on all around me. I thought that I might have died and was in hell, and I was thinking maybe that's what it was.” -- “Maria”

Dissociation involves confusing and upsetting feelings of unreality, unfamiliarity, or disconnection in relation to your mind, body, or surroundings⁶. For example, some people describe being detached from their own emotions, including affection for loved ones, or feeling profoundly ‘strange’, as though they are living life from behind a thick pane of glass. These experiences can cause significant distress^{6,7}, and have been linked with risk of self-harm or suicide⁸⁻¹⁰, and with increased severity¹¹ and incomplete treatment-response¹² of comorbid mental health diagnoses. Many dissociative experiences considered transdiagnostic^{13,14}. For example, dissociation is present at a very high rate in psychotic disorders (potentially up to 50%¹⁵). Crucially, in this context, it may even be instrumental in the development and maintenance of key psychotic symptoms, such as paranoid delusions and auditory hallucinations¹⁶.

[figure not shown]
However, dissociation has traditionally been considered within the context of post-traumatic responses. As a result, a fuller understanding of dissociation as an independent construct – rather than simply as another post-traumatic symptom – has yet to be achieved.

This ‘neglect’¹⁷, and extensive debate within the field¹⁸, has also resulted in a lack of clarity about the precise accepted definition of ‘dissociation’ as a construct^{19,20}. Therefore, in previous work, we delineated a subgroup of common dissociative experiences unified by a core phenomenological experience of a ‘felt sense of anomaly’ (FSA)^{6,21}. We will operationalise the term ‘dissociation’ within this project by focusing on this specific type of dissociative experiences (FSA-dissociation), since this has been demonstrated to be common and transdiagnostic^{22,23}.

What are the psychological maintenance mechanisms of dissociation?

Understanding the psychological mechanisms of a pathological presentation is vital to developing an effective intervention for it. Seminal work developing (now gold standard) cognitive behavioural therapy (CBT) interventions for anxiety disorders²⁴ and PTSD²⁵ have demonstrated the clinical efficacy of identifying, verifying, and then precisely targeting the underlying causal mechanisms of the problem to be treated²⁶. However, much remains unknown about the psychological mechanisms underpinning dissociation. To date, only two experimental studies inferring causality in dissociation have been carried out: one of which was by our group^{27,28}.

In our recent work, we began the process of identifying plausible mechanisms of FSA-dissociation⁴, resulting in a provisional cognitive model of the problem (Figure 1). This model suggests that dissociative experiences are maintained by a two feedback loops. The first is caused by catastrophic appraisals (negative interpretations or beliefs about the dissociative experience), which lead to rumination and counterproductive ‘safety behaviours’ (actions intended to mitigate potential harm), both of which serve to keep attention focused on the dissociation and reinforce interpretations of this experience as threatening. This first loop therefore proposes three possible maintenance mechanisms: catastrophic appraisals of dissociation, perseverative thinking (rumination), and counterproductive safety behaviours.

The second hypothesised feedback loop explains why the appraisals of dissociation are catastrophic in nature – as opposed to benign or benevolent. Across two large studies of online survey⁴ and NHS patient²² (psychosis) respondents, previous data has indicated relationships between dissociation and both high affect intolerance and low self-efficacy. In essence, people who feared shifts or peaks in their mood, and simultaneously felt powerless to manage or cope with challenges, were more likely to have FSA-dissociative experiences – as was indicated by previous qualitative evidence⁶. This second feedback loop therefore suggests two further plausible mechanisms of dissociation: affect intolerance and self-efficacy.

In this project, we have chosen to focus on the three mechanisms with the largest effect sizes from this research: negative cognitive appraisals of the dissociative experience (causal effect 0.73 in a non-clinical group⁴; 0.72 in a psychosis group²²), perseverative thinking (rumination) (0.31⁴; 0.52²²), and affect intolerance (0.26⁴; 0.41²²).

The current study

The aim of this project is therefore to test the three largest psychological contributors to FSA-dissociation as identified in this previous research: cognitive appraisals, rumination, and affect intolerance. Whilst there is evidence that these are all associated with dissociative experiences in the context of psychosis, to date there has been no experimental manipulation of these factors to demonstrate their role in maintaining dissociative difficulties. Evidence of their causal effect on dissociation is required before a translational psychological intervention can be developed.

Using an interventionist-causal approach (experimentally manipulating the factor of interest via attempting to ameliorate it with therapeutic techniques) allows researchers to combine an experimental test of causal relationships with the first stages of treatment development. This project constitutes an intermediate stage along the trajectory of treatment development, in that the primary aim of these three studies will be to demonstrate proof-of-concept for the interventions, in order that a larger study with adequate statistical power to test for causal relationships and treatment efficacy may be carried out.

5. OBJECTIVES AND OUTCOME MEASURES

The primary objective is to determine whether there is sufficient reason to believe that each psychological intervention targets (reduces) the psychological maintenance mechanism (factor) of interest in that study to justify running a larger study. For Study 1 the mechanism of interest will be negative cognitive appraisals of the dissociative experiences; in Study 2, perseverative negative thinking (rumination); and in Study 3, affect intolerance (aversion to the experience of one's own emotions). Therefore, the key outcomes will be measures of these three psychological factors: cognitive appraisals of dissociation, perseverative thinking, and affect intolerance.

Of relevance to future treatment development for dissociation, the secondary objective of this project is to gain a preliminary indication of the effect targeting the above mechanisms has on levels of dissociation – i.e. whether this relationship is causal. There will not be adequate statistical power in these studies to definitively answer this research question. However, data from this study may aid future research by providing initial estimates for sample size calculations.

Since we are interested in further testing and developing the techniques in this project (if this is justified by the data), we will also ask participants for qualitative feedback about their experiences of the intervention and research processes at the end of their participation, and use the experience of running this study to inform which patient-facing logs, worksheets, and diaries may be most useful in developing a future intervention.

These objectives and outcomes are summarised below:

	Objectives	Outcome Measures	Timepoint(s)
Primary	To determine whether the psychological intervention is likely to reduce the psychological maintenance mechanism (factor) of interest (i.e. cognitive appraisals [study 1]; perseverative thinking [study 2]; affect intolerance [study 3]).	Study 1: CAD-P Study 2: PTQ Study 3: AIS	VAS rating: daily (throughout baseline and intervention window), or every other day (throughout follow-up window). Full measure rating: baseline, post-intervention, one month follow-up.
Secondary	To gain a preliminary indication of whether the relationship between the proposed psychological factor (cognitive appraisals; perseverative thinking; affect intolerance) and 'felt sense of anomaly'-type dissociation may be causal.	As above + ČEFSA-14	As above.
Qualitative	To improve the therapy intervention and research processes for use in future treatment development studies.	Qualitative feedback from participants. Audit of which patient-facing therapeutic materials were used.	At one-month follow-up (end of participation).

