11.1. Statistical Analysis

Given the design and sample size, analysis will be descriptive in nature and no hypothesis testing will be carried out. The three studies will be analysed separately according to the following analysis plan.

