12.1.1 Quantitative data

First, patient outcome measures will be presented graphically, and visual and statistical analysis used to assess within- and between-phase data patterns, as per the recommendations for SCEDs⁴⁰.

- Within-phase analysis:
 - level (mean and standard deviation and/or median and interquartile range);
 - trend (visual analysis or whether datapoints are increasing / decreasing);
 - stability (whether 80-90% of datapoints fall within 15% of the mean or median⁴⁰).
- Between-phase analysis:
 - Immediacy of effect (visual analysis);
 - Consistency of data patterns (visual analysis; trend analysis);
 - Overlap between phases (nonoverlap statistics e.g. extended celeration line or two standard deviation band method; as appropriate⁴⁰).

The above information will be used to form a judgement as to whether the data indicates that the intervention is causing a change in outcome measure scores. If so, effect sizes (Tau-U⁴¹) will be calculated.

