11.2. Sample Size Determination

The aim of SCED studies is to use repeated phases with and without the application of the experimental intervention to demonstrate that it is the intervention that is causing the observed effect. In essence, this allows the same participant to contribute both control and intervention data, increasing information about probable cause and effect in contexts where it may not be feasible to run a fully powered randomised controlled trial³¹. General convention suggests that demonstrating changes in the outcome measure after introducing or withdrawing the intervention must be done a minimum of four

times to imply a functional relationship between intervention and effect⁴⁰. Typically, this can be achieved by repeatedly introducing and withdrawing an intervention with the same participant. However, this method is less valid in clinical psychology, where carry-over effects are expected from the intervention, and repeating the intervention may not be practicable. Thus, the multiple-baseline design (MBD) across individuals allows the requisite number of transitions (from intervention to ‘no intervention’ and vice versa) to be achieved, whilst each participant only undergoes the treatment once. Randomising the length of the baseline phase for each participant means that any observed effect cannot be better understood as a function of time elapsed since the baseline assessment or other research procedure. The minimum number of participants required for an MBD study is two, although three or more is typical⁴². Thus, this project will use a sample size of four participants per study, to mitigate against any potential drop out or high levels of missing data.

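### Section 5 offers the data as initial estimates for sample size calculations, but the analysis plan specifies no summary that would deliver them for a group trial, and its one effect size is calculated only after a positive judgement.

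*Combined protocol and SAP*

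**What the plan says.** In section 5, the paragraph on the secondary objective (the effect on dissociation) first concedes that "There will not be adequate statistical power in these studies to definitively answer this research question". It then adds that "data from this study may aid future research by providing initial estimates for sample size calculations". Section 4 places the project as a step towards a larger study with adequate power.

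The analysis is set out in section 11:

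- **Separate studies.** Section 11.1 makes the analysis descriptive and states that "The three studies will be analysed separately according to the following analysis plan". Section 11.2 says that "this project will use a sample size of four participants per study", on the basis of single-case convention: "The minimum number of participants required for an MBD study is two, although three or more is typical".
- **Effect size.** Under 12.1.1, graphs, within-phase level, trend and stability, and between-phase overlap are used to "form a judgement as to whether the data indicates that the intervention is causing a change in outcome measure scores". The next sentence reads "If so, effect sizes (Tau-U⁴¹) will be calculated". No other effect size is named.
- **SDs.** The level of each phase is described by mean and SD and/or median and interquartile range. For the VAS ratings these are SDs over days within one person.
- **Full scales.** The ČEFSA-14 and the mechanism scales are collected from every participant at baseline, post-intervention and follow-up (9.6.1 and Appendix B). Section 11 does not say how they will be summarised as a mean change, a between-person SD or an interval.

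**The concern.** A sample size for a group comparison needs a difference in scale points and a between-person SD, or their ratio. The plan specifies neither. Tau-U measures how far one person's ratings in one phase are displaced from their ratings in another, relative to that person's own day-to-day variation. It holds no scale points and no information on variation between people.

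The condition on Tau-U adds a second problem. Larger apparent changes are more likely to be judged causal, so the Tau-U values that get reported are a favourable subset. A later team taking them as the expected effect would plan too small a study.

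If that team turned to the full scales instead, it would be working from four people per study, with no interval planned to show how little four people determine. The caveat in section 5 is about power to answer the causal question. It does not warn about the precision of planning estimates.

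**Working it through.** **The plan's own figure.** 3 studies × 4 participants = 12, as the synopsis states. It follows convention; no alpha, power, effect or SD is given, so there is no power calculation to reproduce.

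**Precision of an SD.** For normal data, the 95% limits as multiples of the estimate are √(df/χ²₀.₉₇₅) and √(df/χ²₀.₀₂₅), with df = n − 1. For a fixed difference in scale points, required sample size is proportional to SD², so its multipliers are the squares.

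| People | SD multiplier | Sample size multiplier | Ratio |
|---|---|---|---|
| 4 (one study) | √(3/9.348) = 0.57 to √(3/0.2158) = 3.73 | 0.32 to 13.9 | about 43 |
| 12 (pooled, not planned) | 0.71 to 1.70 | 0.50 to 2.88 | about 6 |

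If one of the four drops out, the SD multiplier is 0.52 to 6.29.

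**Precision of an effect at n = 4.** The 95% half-width for a mean change is t₀.₉₇₅,₃/√4 = 1.59 SDs of change. As an illustration (0.8 is an assumed value), an observed standardised change of 0.8 gives t = 0.8 × √4 = 1.6 on 3 df. Inverting the noncentral t gives a 95% CI of −0.40 to 1.91. With 12 people the same observed value gives 0.13 to 1.44.

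**What this does to a later trial.** Assumptions not in the documents: two parallel arms, true difference 0.5 SD, two-sided alpha 0.05, 80% power, normal approximation. Correct size per arm: 2 × (1.960 + 0.842)²/0.5² = 62.8, so 63. Using the SD observed in n people:

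| SD taken from | Percentile of observed SD | Planned per arm | True power |
|---|---|---|---|
| 4 people | 10th | 13 | 25% |
| 4 people | 50th | 50 | 70% |
| 4 people | 90th | 131 | 98% |
| 12 people | 10th | 32 | 52% |
| 12 people | 50th | 60 | 78% |
| 12 people | 90th | 99 | 94% |

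The SD from four people falls below the true value 61% of the time.

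**Why Tau-U does not convert.** For independent normal ratings without trend, tau = 2Φ(d/√2) − 1, where d is the change divided by the *within-person* SD. A change of 10 VAS points with a within-person SD of 10 gives d = 1 and tau = 0.52. A group trial divides by the *between-person* SD. If that SD is 10, the group effect is 10/10 = 1.0 and the size is 2 × (2.802)²/1² = 15.7, so 16 per arm. If it is 20, the effect is 10/20 = 0.5 and the size is 63 per arm. The same Tau-U fits both. (All values here are assumed for illustration.)

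**Selection.** The size of the upward bias cannot be calculated, because 12.1.1 gives no numerical rule for the judgement and does not say whether it is made per participant, per outcome or per study. The direction follows from conditioning on a favourable result.

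**The case against.** The sentence in section 5 is hedged: the data may aid, the estimates are initial, and it comes straight after an admission of inadequate power. It is not in the objectives table or the synopsis, and nothing in section 11 depends on it. The main aim is proof of concept. This stands, and it limits the weight of the point.

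A reader might go further and infer that the studies cannot supply any usable effect or SD. The documents do not support that:

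- Section 12.1.1 already plans phase means and SDs, so a raw VAS change is a subtraction of planned outputs. The condition applies to Tau-U, not to these summaries.
- The within-person SDs could inform a larger repeated-measures or single-case study, and section 4 does not say that the larger study will be a parallel-group trial.
- The full scales are collected from all 12 people, so a pooled baseline SD for the ČEFSA-14 is obtainable. It would describe people entering with a score of 39 or above, and section 11.1 does not plan to pool.

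A reader might also infer that four per study is a sample size error, or that Tau-U is a poor choice because very different raw changes can share one value. Neither follows. Four is justified by single-case convention. Any standardised effect is unchanged when the change and its SD are scaled together. The difficulty specific to Tau-U here is that its yardstick is variation within a person.

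**Conclusion.** The point holds as a gap between a stated use of the data and the planned summaries. Nothing in section 11 commits the team to a mean change, between-person SD or interval that a group trial could be sized on. The one named effect size lacks the needed information and is reported selectively. Any such estimate derived later would be very imprecise: about 43-fold uncertainty in required sample size from one study of four, about 6-fold from all 12.

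The ranges assume roughly normal scores and a planning difference fixed in scale points. The power figures also assume a two-arm trial with a true effect of 0.5 SD. The selection argument gives a direction only.

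No allocation, measurement or conclusion of the present studies changes. The consequence falls on the later study, and only if its team relies on these figures alone. It is worth correcting because the correction is cheap.

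**What to change.** In 12.1.1:

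- Remove the condition on Tau-U. Report Tau-U and the A₁-to-B₁ change in VAS points for every participant with analysable A₁ and B₁ phases, meaning at least five datapoints in each as section 11.6 requires, whatever the visual judgement.
- For the full scales, including the ČEFSA-14, report the mean change and its SD for each study with 95% CIs. These are descriptive and do not conflict with section 11.5, which rules out significance testing.

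In section 5, replace the sentence on sample size with, for example: *These studies will provide descriptive estimates of change and variability, reported with 95% confidence intervals. With four participants per study they will be very imprecise and will not be used alone to set the size of a later study.*

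The cost is a few extra summaries from data already being collected, and a stated use of the data that becomes slightly less favourable. No further participants, visits or measures are needed.
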